03 APR 2020

\_\_\_\_\_  
Date dd-MON-yyyy

Study Type: Observational

Estimated Enrollment: 1000 participants (200 per site)

Observational Model: Cohort

Time Perspective: Prospective

Timelines:

Actual Study Start Date: April 15, 2020

[figure not shown]
Estimated Primary Completion Date: July 31, 2020

Estimated Study Completion Date: December 31, 2020

## Introduction

The 2019-nCoV IgG/IgM Rapid Test Cassette (Whole Blood/Serum/Plasma) is a qualitative membrane based immunoassay for the detection of IgG and IgM antibodies to 2019-nCoV in whole blood, serum or plasma specimen. This test consists of two components, an IgG component and an IgM component. In the IgG component, anti-human IgG is coated in IgG test line region. During testing, the specimen reacts with 2019-nCoV antigen-coated particles in the test cassette. The mixture then migrates upward on the membrane chromatographically by capillary action and reacts with the anti-human IgG in IgG test line region, if the specimen contains IgG antibodies to 2019-nCoV. A colored line will appear in IgG test line region as a result of this. Similarly, anti-human IgM is coated in IgM test line region and if specimen contains IgM antibodies to 2019-nCoV, the conjugate-specimen complex reacts with anti-human IgM. A colored line appears in IgM test line region as a result. Therefore, if the specimen contains 2019-nCoV IgG antibodies, a colored line will appear in IgG test line region. If the specimen contains 2019-nCoV IgM antibodies, a colored line will appear in IgM test line region. If the specimen does not contain 2019-nCoV antibodies, no colored line will appear in either of the test line regions, indicating a negative result. To serve as a procedural control, a colored line will always appear in the control line region, indicating that the proper volume of specimen has been added and membrane wicking has occurred.

Figure 1: Test principle

As shown in illustration in Fig. 1, the specimen (A) migrates via capillary action along the membrane to react with the gold conjugate (B). 2019-nCoV IgG or/and IgM present in the specimen binds to the conjugate, forming a colored Novel coronavirus antibody-antigen complex. The mouse anti-human IgG and mouse anti-human IgM immobilized in the test zone of the membrane captures the test region (C) and test region (D). The formation of a visible colored line in the test region indicates a positive result (C) or (D). The absence of a colored line in the test zones suggests a negative result. In the control zone of the membrane, immobilized reagents capture colored conjugate regardless of test specimen composition. The resulting visible colored band (E) confirms control line.

Incubation Time: RESULTS AT 10 MINUTES

Storage:

Store the test at 2-30°C. Do not freeze.

[figure not shown]
**Active ingredient list:**

- Mouse anti-human IgG (capture reagent)
- Mouse anti-human IgM (capture reagent)
- Mouse IgG
- Goat anti-mouse IgG
- 2019-nCov antigen (detection reagent)

**Inactive ingredients list:**

- Adhesive plastic backing
- Buffer
- Label pad
- Absorbent pad
- Sample pad
- Nitrocellulose membrane
- Desiccant (in pouch)
- Pouch
- Sample dropper

1.2/Assay procedure:

- 1) Wash the patient's hand with soap and warm water or clean with an alcohol swab. Allow to dry. Fig 1 and Fig 2.
- 2) Massage the hand without touching the puncture site by rubbing down the hand towards the fingertip of the middle or ring finger
- 3) Puncture the finger with a sterile lancet. Wipe away the first sign of blood. Fig 3.
- 4) Gently rub the hand from wrist to palm to finger to form a rounded drop of blood over the puncture site. Fig 4.
- 5) Add the Fingerstick Whole Blood specimen to the test by using a capillary tube: Touch the end of the capillary tube to the blood until filled to approximately 20µL. Avoid air bubbles. Fig 5.

- 6) Place the bulb onto the top end of the capillary tube, then squeeze the bulb to dispense the wholeblood to the specimen well of the test cassette. Fig 6.
- 7) Dispense two drops of diluent to the specimen well of the test cassette. Fig 7.
- 8) Read test results after 10 minutes. Fig 8.

**Precautions:**

Bring tests, specimens, buffer, and/or controls to room temperature (15-30°C) before use.

Bring the pouch to room temperature before opening. Remove the test cassette from the sealed pouch and use it within one hour.

Place the test cassette on a clean and level surface.

Testing should be performed immediately after specimen collection. Do not leave the specimens at room temperature for prolonged periods. Whole blood collected by venipuncture should be stored at 2-8°C if the test is to be run within 2 days of collection. Do not freeze whole blood specimens. Whole blood collected by fingerstick should be tested immediately.

Bring specimens to room temperature prior to testing. Frozen specimens must be completely thawed and mixed well prior to testing. Specimens should not be frozen and thawed repeatedly. If specimens are to be shipped, they should be packed in compliance with local regulations covering the transportation of etiologic agents.

EDTA K2, Heparin sodium, Citrate sodium and Oxalate potassium can be used as anticoagulants.

**Interpretation of the results:**

**IgG POSITIVE:**\* Two colored lines appear. One colored line should always appear in the control line region (C) and another line should be in the IgG line region.

**IgM POSITIVE:**\* Two colored lines appear. One colored line should always appear in the control line region (C) and another line should be in the IgM line region.

**IgG and IgM POSITIVE:**\* Three colored lines appear. One colored line should always appear in the control line region (C) and two test lines should be in the IgG line region and IgM line region.

\*NOTE: The intensity of the color in the test line regions may vary depending on the concentration of 2019-nCoV antibodies present in the specimen. Therefore, any shade of color in the test line region should be considered positive.

**NEGATIVE:** One colored line appears in the control line region (C). No line appears in the IgG region and IgM region.

**INVALID:** Control line fails to appear. Insufficient specimen volume or incorrect procedural techniques are the most likely reasons for control line failure. Review the procedure and repeat the test with a new test. If the problem persists, discontinue using the test kit immediately and contact your local distributor.

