### **Study Population**

Patients or health professionals already tested positive for the viral RNA from nasopharyngeal swabs by RT-PCR. Patients or health professional who are suspected of being infected with SARS-CoV-2 in the hospital. Patients who are considered at high risk for infection and eligible for active therapy and major surgery.

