#### **2. Confirmed cases**

Patients or subjects with positive RT-PCR for SARS-CoV-2. On the basis of meeting the criteria for suspected cases, sputum, throat swabs, lower respiratory tract secretions, and other specimens were tested by real-time RT-PCR for positive nucleic acid detection of new coronavirus; or viral gene sequencing was highly homologous with known new coronaviruses. Patients positive are serially tested with SARS-CoV-2 IgM / IgG Rapid Test to evaluate the immune response in IgG negative patients and the reliability of the test in those patients who develop clinical signs of SARS-CoV-2 during the trial.

3. Patients who are considered at high risk for infection and eligible for active therapy and major surgery

- Frailty (age and multiple comorbidities) planned to receive a standard systemic anticancer treatment comprising chemotherapy and/or immunotherapy and/or radiation therapy or to receive an experimental treatment
- Major surgery or surgery after neoadjuvant chemotherapy and or chemo/radiotherapy

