## Clinical considerations

All patients with epidemiologic history and/or clinical manifestations suspected for COVID will be proposed, according to the clinical judgement, for RT-PCR test for positive nucleic acid detection, irrespective of serological evidence.

All patients tested as IgM positive will have a confirmatory real-time RT-PCR test for positive nucleic acid detection of new coronavirus on sputum, throat swabs, lower respiratory tract secretions, and other specimens.

The 2019-nCov IgG/IgM Rapid Test Cassette (Whole Blood/Serum/Plasma) will be repeated in patients IgM positive for confirming the subsequent IgG positivity.

The tests will be performed locally in each hospital laboratory.

The ASST of Cremona laboratory could perform:

- [name], UO Laboratorio Analisi – ASST di Cremona: SARS-CoV-2 IgG/IgM Rapid Test Cassette (Whole Blood/Serum/Plasma) also for other sites. 1 ml of plasma will be needed;
- [name] SMeL849 – ASST di Cremona: *multiplex* immunoassay protein quantitation related to markers of inflammation and immunity (IL-6, TNF, INF $\gamma$ , IL1, IL-2, ect). 2.5 ml of plasma will be needed.

The lab responsible person in Milano IEO is:

Dr.ssa [name]  
Divisione di Medicina di Laboratorio  
Istituto Europeo di Oncologia

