## Statistical Plan

All data recorded will be summarized in tables, graphs and listings. In general, categorical data will be presented using counts and percentages, whilst continuous variables will be presented using the mean, standard deviation, median, minimum, maximum and number of patients.

In tabulations, denominators for calculation of percentages will be taken as the number of non-missing responses.

Primary end-point, the accuracy of tests, will be sensitivity and specificity and they will be calculated for all tests and compared with the appropriate statistical test.

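### The plan does not mask the cassette reader to RT-PCR status, so sensitivity in already-confirmed cases may be overestimated, and specificity too where a negative RT-PCR is known first

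*Combined protocol and SAP*

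**What the plan says.** The Introduction describes a positive as a coloured line that can be seen in a test region; no instrument reader is mentioned. Under Interpretation of the results, line intensity is said to vary with antibody concentration, and the rule is that "any shade of color in the test line region should be considered positive".

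The Study Population section opens with "Patients or health professionals already tested positive for the viral RNA from nasopharyngeal swabs by RT-PCR", and the second inclusion group, Confirmed cases, is defined as "Patients or subjects with positive RT-PCR for SARS-CoV-2". The same section has positive patients tested serially with the cassette. Clinical considerations adds that the cassette is repeated in IgM-positive patients to confirm that IgG positivity follows.

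On the order of the tests, Clinical considerations gives two rules. For the cassette-positive: "All patients tested as IgM positive will have a confirmatory real-time RT-PCR test for positive nucleic acid detection of new coronavirus". For those with a suspicious history or symptoms, RT-PCR is proposed "according to the clinical judgement, for RT-PCR test for positive nucleic acid detection, irrespective of serological evidence", with no order relative to the cassette. On location: "The tests will be performed locally in each hospital laboratory".

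The Statistical Plan states: "Primary end-point, the accuracy of tests, will be sensitivity and specificity". No section says what the reader may know, asks for a second reading, or provides for adjudication of doubtful lines.

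**The concern.** The any-shade rule fixes the threshold, but someone must still decide whether a trace is visible at all. A reader who knows that the participant is RT-PCR positive, or who expects IgG to appear on a retest, is more likely to see a doubtful line. That is review bias: the reference result leaks into the reading of the index test. It bears on the primary accuracy endpoint, it does not shrink as enrolment grows, and if nobody records what the reader knew, no later analysis can separate it out.

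**Working it through.** **The plan's own figures.** The plan gives no figure for reading error. The nearest numbers are the earlier performance results in Tables 1 and 2 (70 specimens). For IgM, 17/20 = 85.0% sensitivity (exact 95% interval 62.1% to 96.8%) and 48/50 = 96.0% specificity (86.3% to 99.5%); both reproduce. Across both tables all point estimates and five of six intervals reproduce. The exception, the lower limit for IgG sensitivity (86.0% printed, 83.2% by the two-sided exact method), has no bearing here. The tables give counts only and say nothing about line intensity.

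**Who can know what at the reading.**

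| Participants | RT-PCR known before the reading? | Measure exposed |
|---|---|---|
| Confirmed cases | Yes, positive, by entry criterion | Sensitivity |
| Serial retests of positives | Yes, with earlier cassette results | Sensitivity, if repeats are analysed (not stated) |
| IgM-positive, no earlier RT-PCR | No; confirmatory RT-PCR follows | Neither, at the first reading |
| Suspected cases | Order not stated | Sensitivity if a positive is known; specificity if a negative is known |
| High-risk patients due for therapy or surgery | No RT-PCR required at entry; order not stated | As for suspected cases |

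Only the first two rows are documented as known, and both concern positives. No entry group is defined by a negative RT-PCR.

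**Illustration of size (assumed inputs).** None of these inputs is in the documents:
- f: share of readings with an equivocal line, taken as 2%, 5% or 10%;
- q: probability that a masked reader calls an equivocal line positive; q = 1 means the any-shade rule is followed perfectly;
- k+ and k−: shares of PCR-positives and PCR-negatives whose status is known at the reading.

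Assume, as an extreme, that a reader who knows the status always calls an equivocal line in its favour: positive in a known positive, negative in a known negative. Then

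- rise in sensitivity = f × k+ × (1 − q)
- rise in specificity = f × k− × q

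Rise in sensitivity, in percentage points, with k+ = 1:

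| q | f = 2% | f = 5% | f = 10% |
|---|---|---|---|
| 0.5 | 1.0 | 2.5 | 5.0 |
| 0.8 | 0.4 | 1.0 | 2.0 |
| 0.95 | 0.1 | 0.25 | 0.5 |
| 1.0 | 0 | 0 | 0 |

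For example, 0.10 × 1 × (1 − 0.5) = 0.05, or 5 points. If only half the positives are known (k+ = 0.5), every entry halves.

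With k− = 0, specificity does not move in any cell. If half the negatives were known (k− = 0.5) and q = 0.95, the rise would be 0.02 × 0.5 × 0.95 = 0.95 points to 0.10 × 0.5 × 0.95 = 4.75 points. That requires readers to break the any-shade rule once they know the RT-PCR was negative.

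**The case against.** The strongest reply is that the any-shade rule protects the study. It removes most discretion, and a reader who dismisses a faint line in a known negative has departed from the instructions. Followed strictly, the rule pushes specificity down, not up. This stands, and it narrows the problem to whether a very faint line is visible at all.

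A reader might infer that the design inflates sensitivity and specificity alike. The documents do not support that. Prior knowledge is documented only for RT-PCR positives, and for IgM-positive participants not already tested, the RT-PCR comes after the cassette. A false-positive IgM line in that group is read before its reference result exists.

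A reader might also take a size from Table 2: re-reading one or two of the 3 IgM misses would move 17/20 to 18/20 or 19/20 (85% to 90% or 95%), and dropping the 2 false positives would move 48/50 to 50/50 (96% to 100%). Nothing says that those cassettes had faint lines. Steps of 1/20 = 5 points and 1/50 = 2 points belong to the earlier 70-specimen study, not to a trial planning 1,000 participants.

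Finally, testing in local hospital laboratories does not show that the reader sees the RT-PCR result. That is true, but nothing prevents it either. The written procedure is a fingerstick, tested at once and read after 10 minutes, so the reader may be beside a participant whose status is known.

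**Conclusion.** The concern holds in a limited form. The reading is visual, part of the population is known to be RT-PCR positive beforehand, positives are retested with an expected result, and no masking is specified. Sensitivity in already-confirmed cases may be overestimated. An upward bias in specificity is possible only where a negative RT-PCR is known before the reading, which the unstated test order leaves open.

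The size cannot be computed from the documents. The illustrative range of 1 to 5 points rests on 2% to 10% equivocal lines, half called positive under masking, all positives known, and known status always settling the call. It falls to 0 under perfect use of the any-shade rule. The plan should be changed on this point because what the reader knew cannot be reconstructed if it was not recorded.

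**What to change.** In Clinical considerations, state that specimens go to the hospital laboratory under a study code. Existing laboratory staff then record and lock the timed IgG and IgM readings before RT-PCR status or enrolment group is available to them. Retests should carry a new code so that the earlier result is not visible. Record the date and time of both tests, so that their order is known for every participant.

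Coded labels do not mask a reader at the bedside. Any cassette read there, or with status known, should be flagged on the result form.

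In the Statistical Plan, report sensitivity and specificity separately for masked and unmasked readings, and say whether repeat readings enter the analysis. Simply excluding unmasked readings is not advisable: it could remove much or all of the confirmed-case group and leave sensitivity poorly estimated. A difference between the two sets would also partly reflect case mix, so it should not be read as a direct measure of the bias.

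The cost is a small change in sample labelling and one or two extra fields on the result form at five sites (1,000 participants at 200 per site). No additional reader is needed where the laboratory does the reading.

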**Limitations:**

The 2019-nCoV IgG/IgM Rapid Test Cassette (Whole Blood/Serum/Plasma) is for in vitro diagnostic use only. This test should be used for detection of IgG and IgM antibody to 2019-nCoV in whole blood, serum or plasma specimens. Neither the quantitative value nor the rate of increase in the concentration of IgG or IgM antibodies to 2019-nCoV can be determined by this qualitative test.

The 2019-nCoV IgG/IgM Rapid Test Cassette (Whole blood/Serum/Plasma) will only indicate the presence of IgG and IgM antibodies to 2019-nCoV in the specimen and should not be used as the sole criteria for the diagnosis of 2019-nCoV infections.

As with all diagnostic tests, all results must be considered with other clinical information available to the physician.

If the test result is negative and clinical symptoms persist, additional follow-up testing using other clinical methods is suggested. A negative result at any time does not preclude the possibility of 2019- nCoV infection.

The hematocrit level of the whole blood can affect the test results. Hematocrit level needs to be between 25% and 65% for accurate results.

## Performance study

### ***Accuracy, specificity, sensitivity and correlation***

The 2019-nCoV IgG/IgM Rapid Test Cassette (Whole Blood/Serum/Plasma) was compared with a leading commercial PCR; the results show that 2019-nCoV IgG/IgM Rapid Test Cassette (Whole Blood/Serum/Plasma) has a high sensitivity and specificity. Results for IgG and IgM are shown in Table 1 and 2 respectively.

*Table 1: Performance of IgG specimen*

Method		PCR		Total result
Rapid test cassette	Results	Positive	Negative	
	Positive	20	1	21
	Negative	0	49	49
Total result		20	50	70

Specificity = 98.0% (95%CI: 89.4%~99.9%);

Sensitivity = 100% (95%CI: 86.0%~100%);

Accuracy = 98.6% (95%CI: 92.3%~99.96%).

*Table 2: Performance of IgM specimen*

Method		PCR		Total result
Rapid test cassette	Results	Positive	Negative	
	Positive	17	2	19
	Negative	3	48	51
Total result		20	50	70

Specificity = 96.0% (95%CI: 86.3%~99.5%);

Sensitivity = 85.0% (95%CI: 62.1%~96.8%);

Accuracy = 92.9% (95%CI: 84.1%~97.6%).

The 2019-nCov IgG/IgM Rapid Test Cassette (Whole Blood/Serum/Plasma) products have been compared with a commercial PCR using clinical specimen. The results show that the relative sensitivity of the 2019-nCov IgG/IgM Rapid Test Cassette (Whole Blood/Serum/Plasma) is 98.6% and the relative specificity is 92.7%.

Refer to data on investigator brochure for other technical data related to interference and cross-reactivity.

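### Does the misstated prior performance of the cassette (sensitivity 98.6%, specificity 92.7%) undermine the validation planned in this trial?

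*Combined protocol and SAP*

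**What the plan says.** The Performance study section, under accuracy, specificity, sensitivity and correlation, compares each antibody line with PCR in a two-by-two table of 20 PCR-positive and 50 PCR-negative specimens.

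- Table 1 (IgG) has the rows "Positive 20 1 21" and "Negative 0 49 49". Below it stand specificity 98.0%, "Sensitivity = 100% (95%CI: 86.0%~100" per cent) and "Accuracy = 98.6% (95%CI: 92.3%~99.96" per cent).
- Table 2 (IgM) has 17 true positives, 2 false positives, 3 false negatives and 48 true negatives. Below it stand specificity 96.0%, "Sensitivity = 85.0% (95%CI: 62.1%~96.8" per cent) and "Accuracy = 92.9% (95%CI: 84.1%~97.6" per cent).

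The closing sentence then gives one pair for the whole cassette: "relative sensitivity of the 2019-nCov IgG/IgM Rapid Test Cassette (Whole Blood/Serum/Plasma) is 98.6% and the relative specificity is 92.7" per cent. It states no sample size and cites no source.

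The Aim of the study is to validate the assay, with RT-PCR as the gold standard. The Statistical Plan says that sensitivity and specificity will be calculated for all tests and compared with a suitable test. It names no performance goal, null value or historical comparator. The front page gives an estimated enrolment of 1000 (200 per site) without a calculation.

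**The concern.** A validation study should describe correctly what is already known about the device. Here the summary pair conflicts with the tables printed above it. A reader who took that pair as the performance to be confirmed would be misled in two ways:

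- **Sensitivity.** 98.6% implies 100 − 98.6 = 1.4 misses per 100 PCR-positives. Table 2 implies 100 − 85 = 15 for the IgM line, and the Clinical considerations section sends IgM-positive patients for confirmatory RT-PCR.
- **Specificity.** 92.7% implies 100 − 92.7 = 7.3 false positives per 100 PCR-negatives. The tables imply 2 (IgG) or 4 (IgM).

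If the trial's estimates were judged against the pair, an observed sensitivity of 90% would look like a failure although it exceeds the IgM figure. A specificity of 94% would look like a success although it lies below both tabled values. In addition, the IgG sensitivity interval looks tighter than 20 specimens allow.

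**Working it through.** **Inputs.** All counts come from Tables 1 and 2. Both have 20 PCR-positives, 50 PCR-negatives and 70 in total.

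**1. Reproduce the tabled values.** Sensitivity = TP/20, specificity = TN/50, accuracy = (TP + TN)/70. Intervals are two-sided 95% exact (Clopper-Pearson).

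| Quantity | Count | Estimate | Exact 95% interval | Printed interval |
|---|---|---|---|---|
| IgG sensitivity | 20/20 | 100% | 83.2 to 100 | 86.0 to 100 |
| IgG specificity | 49/50 | 98.0% | 89.4 to 99.9 | 89.4 to 99.9 |
| IgG accuracy | 69/70 | 98.6% | 92.3 to 99.96 | 92.3 to 99.96 |
| IgM sensitivity | 17/20 | 85.0% | 62.1 to 96.8 | 62.1 to 96.8 |
| IgM specificity | 48/50 | 96.0% | 86.3 to 99.5 | 86.3 to 99.5 |
| IgM accuracy | 65/70 | 92.9% | 84.1 to 97.6 | 84.1 to 97.6 |

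All six estimates and five of the six intervals agree.

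**2. The odd interval.** For 20/20 the two-sided exact lower limit is 0.025^(1/20) = 0.832. The one-sided 95% limit is 0.05^(1/20) = 0.861. The printed 86.0% has tail probability 0.86^20 = 0.049, so it is in effect a one-sided limit without a label. The difference is 86.0 − 83.2 = 2.8 points.

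**3. Can the summary pair be derived?** A sensitivity on 20 specimens moves in steps of 5 points (95% or 100%), so 98.6% cannot occur. A specificity on 50 moves in steps of 2 points (92% or 94%), so 92.7% cannot occur. Other readings also fail:

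- Tables pooled: sensitivity (20 + 17)/40 = 92.5%, specificity (49 + 48)/100 = 97.0%.
- Both lines required: sensitivity 17/20 = 85%, specificity 49/50 to 50/50 = 98% to 100%.
- Positive and negative predictive values: IgG 20/21 = 95.2% and 49/49 = 100%; IgM 17/19 = 89.5% and 48/51 = 94.1%.

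98.6% equals the IgG accuracy exactly. 92.7% is 0.2 points from the IgM accuracy, and no count out of 20, 40, 50, 70, 100 or 140 rounds to it. Mislabelled accuracy figures with one miscopied digit are therefore the likely explanation, but that is an inference.

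**4. The like-for-like comparison.** The sentence describes the whole cassette. Under Interpretation of the results, a negative reading needs both test lines absent, so the matching quantity is positivity on either line. Assume that both tables use the same 70 specimens. IgG alone detects all 20 positives, so sensitivity is 20/20 = 100%. False positives number 2 if the IgG one is among the two IgM ones, and 3 if it is not. Specificity is therefore 48/50 = 96% or 47/50 = 94%. The stated pair is lower by 100 − 98.6 = 1.4 points on sensitivity, and by 94 − 92.7 = 1.3 to 96 − 92.7 = 3.3 points on specificity.

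**5. Does anything in the plan use the pair?**

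- Statistical Plan: no target, null value or margin, and no comparison with prior data.
- Enrolment: 1000, not derived from any performance figure.
- Aim and Primary endpoints: the reference is RT-PCR, not an earlier estimate.
- Clinical considerations: neither figure is cited. RT-PCR is also to be proposed to suspected patients whatever their serology, subject to clinical judgement, so a miss on the IgM line does not by itself mean that a suspected case goes unconfirmed.

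**The case for a change.** The strongest case for a change is that the error is certain, can be checked within one section and would take one paragraph to correct. Accuracy of the assay is a primary endpoint, and the section holds the only prior performance data in the document. A single pair also hides a 15-point gap in sensitivity between the lines (100% against 85.0%). An uncorrected sentence could be carried into the trial report as the manufacturer's claim. The Statistical Plan does not say what the tests will be compared with, so someone might reach for the summary pair.

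The arithmetic stands in full: the pair does not follow from the tables, and the 86.0% limit does not match its neighbours. The consequences do not stand. The pass-or-fail scenarios need a decision rule that the documents do not contain. The contrast of 1.4 with 15 misses sets a cassette-level figure against one line. The value of 94%, said to be below both tabled values, lies within the either-line range. The full tables, with the 85.0% and its wide interval, come before the summary sentence, so anyone who wants a historical comparison has the right numbers at hand. Requiring a formal comparison with Tables 1 and 2 would add an analysis that the trial does not need in order to estimate accuracy against RT-PCR.

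**Conclusion.** This is a clerical slip in background device text, and no change to the plan follows. The summary pair is not derivable from the tables, and one lower limit is 2.8 points too high for the two-sided exact method used for the other five intervals. The effect on the trial is nil: no endpoint, sample size, test or decision rule uses 98.6%, 92.7% or 86.0%. At cassette level the misstatement amounts to 1.4 points on sensitivity and 1.3 to 3.3 points on specificity, and both make the device look worse, not better. An analyst who cites prior performance would sensibly take it line by line from Tables 1 and 2.

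This rests on three assumptions: that both tables describe the same 70 specimens, as the identical totals suggest; that the summary sentence refers to those specimens and not to an unreported data set; and that no performance goal is set from the summary pair later. If one were, the discrepancy would have to be resolved before that goal was used.
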